6.4.3 OS and PFS definitions

OS is defined as the time from first dose of study treatment to death due to any cause. Subjects without documented death at the time of the final analysis will be censored at the date of the last follow-up.

PFS is defined as the time from first dose of study treatment to the first documented disease progression based on RECIST v.1.1 or death due to any cause, whichever occurs first.

6.4.4 irRECIST

Immunotherapeutic agents such as MK3475 (pembrolizumab) may induce antitumor effects by potentiating endogenous cancer-specific immune responses. The response patterns observed with these compounds may be different to the typical time course of responses seen with classical cytotoxic agents, and can manifest a clinical response after an initial increase in tumor burden or even the appearance of new lesions. Standard RECIST v.1.1 may, therefore, not provide a precise response assessment of immunotherapeutic agents such as MK3475 (pembrolizumab) .

irRECIST is RECIST v.1.1 adapted to account for the unique tumor response seen with immunotherapeutic agents. In this way, in subjects who have initial evidence of radiological disease progression by RECIST v.1.1, it is at the discretion of the Investigator whether to continue a subject on study treatment until repeat imaging is obtained. Subjects may receive study treatment and tumor assessment should be repeated at least four weeks later in order to confirm disease progression by irRECIST. Any subject deemed clinically unstable should be discontinued from trial treatment at first radiologic evidence of disease progression and is not required to have repeat imaging for disease progression confirmation. Clinical stability is defined as the following:

- Absence of symptoms and signs indicating clinically significant disease progression, including worsening of laboratory values.

- No decline in ECOG performance status.
- Absence of rapid progression of disease.
- Absence of progressive tumor at critical anatomical sites (e.g., cord compression) requiring urgent alternative medical intervention.

In determining whether or not the tumor burden has increased or decreased per irRECIST, the local site Investigator should consider all target and non-target lesions as well as any incremental new lesion(s). Scenarios where disease progression is confirmed at repeat imaging if any of the following occur by irRECIST:

- Tumor burden remains $\geq 20\%$ and at least 5 mm absolute increase compared to nadir.
- Non-target disease resulting in initial disease progression is worse (qualitative assessment).
- New lesion resulting in initial disease progression is worse (qualitative assessment).
- Additional new lesion(s) since last evaluation.
- Additional new non-target progression since last evaluation.

If repeat imaging confirms disease progression due to any of the scenarios listed above, subjects will be discontinued from study therapy. If repeat imaging does not confirm disease progression by irRECIST and the subject continues to be clinically stable, treatment may continue and follow the regular imaging schedule.

*Note: If a subject with confirmed radiographic progression per irRECIST, but the subject is achieving a clinically meaningful benefit, and there is no further increase in the tumor burden at the confirmatory tumor imaging, an exception to continue treatment may be considered following consultation with the Sponsor. In this case, if treatment is continued, tumor imaging should continue to be performed following the intervals as outlined in **Appendix 1**.*

*Note: In subjects who discontinue study treatment without documented disease progression, every effort should be made to continue monitoring their disease status by tumor imaging following the intervals as outlined in **Appendix 1** until the start of new anti-cancer treatment, disease progression, death, or the end of the study, whichever occurs first.*

6.5 Safety and tolerability assessments

6.5.1 Laboratory assessments

Laboratory tests will be performed in accordance to local standard treatment and clinical indications. These values will include:

- Hematological test [hemoglobin, hematocrit, red blood cell count, platelet count, white blood cell (WBC) with differential count (ANC, lymphocytes, monocytes, eosinophils and basophils)], coagulation, chemistry with renal function analysis (serum creatinine), liver function [AST, ALT, alkaline phosphatase (ALP), gamma-glutamyl transferase (GGT), total and direct bilirubin], glucose, sodium, potassium, calcium, chloride, magnesium, uric acid, total protein, albumin, and lactate dehydrogenase.
- Urinalysis (specific gravity, pH, glucose, protein, ketones, and blood).
- Thyroid function testing [thyroid-stimulating hormone (TSH), free T3, and free T4].
- HIV serology.
- HBV serology [HBsAg, anti-HBsAg].
- HCV serology (anti-HCV). In patients with a positive anti-HCV, HCV RNA detection and quantification by PCR will be additionally performed.

6.5.2 Pregnancy and assessment of fertility

MK3475 (pembrolizumab) and eribulin may have adverse effects on a fetus in utero. Only female patients of childbearing potential must undergo a pregnancy test at screening (serum pregnancy test within 14 days before Cycle 1, Day 1) to confirm eligibility in the trial and thereafter every two cycles (cycle 3 day 1, cycle 5 day 1, cycle 7 day 1, etc.) (urine pregnancy test) and at EOT visit. In case an additional pregnancy test is indicated during the trial, a serum test should be performed.

Post-menopausal status is defined as:

- Prior bilateral oophorectomy.
- Age \geq 60 years.
- Age $<$ 60 years and amenorrhea for 12 or more months (in the absence of chemotherapy, tamoxifen, toremifene, or ovarian suppression), and with a documented estradiol level in the postmenopausal range according to local institutional/laboratory standard.

Non-pregnant, non-breast-feeding women may be enrolled if they are willing to use a highly effective, non-hormonal form of contraception (such as surgical sterilization, total abstinence or placement of an intrauterine device (IUD) or intrauterine system (IUS) or two effective forms of non-hormonal contraception, or are considered highly unlikely to conceive (post-menopausal; not

heterosexually active for the duration of the study) [35]. The following non-hormonal methods of contraception are acceptable:

- Condom with spermicidal foam/gel/film/cream/suppository.
- Occlusive cap (diaphragm or cervical/vault caps) with spermicidal foam/gel/film/cream/suppository.

Subjects should start using birth control from screening throughout the study period up to 120 days after the last dose of treatment with MK3475 (pembrolizumab) .

In case of pregnancy, the patient must permanently stop study treatment immediately, withdraw from the trial, and the pregnancy must be reported within 24 hours to the Sponsor. The site will contact the subject at least monthly and documented the subject's status until the pregnancy has been completed or terminated. The outcome of pregnancy will be reported to the Sponsor without delay and within 24 hours if the outcome is a serious adverse experience (e.g., death, abortion, congenital anomaly, or other disabling or life-threatening complication to the mother or newborn). The study Investigator will make every effort to obtain permission to follow the outcome of the pregnancy and report the condition of the fetus or newborn to the Sponsor.

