| | 
12. Uncontrolled hyper/hypothyroidism or type 1 diabetes mellitus (T1DM). Patients with hypothyroidism stable on hormone replacement will not be excluded from the trial. Patients with controlled T1DM on a stable insulin regimen may be eligible for this study.
 
13. Active autoimmune disease that has required systemic treatment in past 2 years (i.e., with use of disease modifying agents, corticosteroids, or immunosuppressive drugs).
 
Note: Replacement therapy (e.g., thyroxine, insulin, or physiologic steroid replacement therapy (≤ 10 mg prednisone daily) for adrenal or pituitary insufficiency, etc.) is not considered a form of systemic treatment.
 
14. Prior allogenic stem cell or solid organ transplantation.
 
15. Active/history of pneumonitis requiring treatment with steroids or active/history of interstitial lung disease.
 
16. Active uncontrolled infection at the time of screening
 
17. Active tuberculosis.
 
18. Current known infection with HIV.
 
19. Active hepatitis B (HBV) [patients with negative hepatitis B surface antigen (HBsAg) test and a positive antibody to HBsAg (anti-HBsAg) test at screening are eligible] or hepatitis C (HCV) [patients with a positive antibody to hepatitis C (anti-HCV) are eligible only if polymerase chain reaction (PCR) is negative for virus hepatitis C RNA].
 
20. Patients have any other concurrent severe and/or uncontrolled medical condition that would, in the Investigator's judgment contraindicate patient participation in the clinical study.
 
21. Treatment with systemic steroids (standard premedication for chemotherapy/contrast reactions, inhaled steroids, and local applications are allowed) or another immunosuppressive agent within seven days prior to study treatment initiation.
 |
|--|--|

| | |
|--------------------------|--|
| | 
22. Has received live vaccines within 30 days prior to first dose of study treatment.
 
23. Women of child-bearing potential, defined as all women physiologically capable of becoming pregnant, are not allowed to participate in this study unless they are using highly effective methods of contraception during dosing and up to 120 days after study drugs discontinuation.
 |

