3 STUDY DESIGN

3.1 Description of study design

This is a multicenter, open-label, phase II clinical trial to evaluate the efficacy and safety of the combination of MK3475 (pembrolizumab) and eribulin in HR-positive/HER2-negative MBC patients previously treated with anthracyclines and taxanes.

The study population consists of female patients age \geq 18 years with advanced HR-positive/HER2-negative breast cancer who have received at least one, but not more than two, prior chemotherapeutic regimens for treatment of locally recurrent and/or metastatic disease. Prior therapy must have included an anthracycline and a taxane in any combination or order and either in the early or metastatic disease setting unless contraindicated for a given patient. Previous anti-hormonal therapy in the metastatic disease setting is mandatory.

In the absence of disease progression or unacceptable toxicity, treatment with MK3475 (pembrolizumab) and eribulin will continue based on physician criteria. MK3475 (pembrolizumab) and eribulin may be discontinued for toxicity independently of each other in the absence of disease progression.

A participant must be discontinued from study treatment but continue to be monitored in the study for any of the following reasons:

- Completion of 35 treatments (approximately 2 years) with pembrolizumab. Please see the specific conditions at section 5.3.5.

Note: The number of treatments is calculated starting with the first dose. Participants who stop the combination or pembrolizumab after receiving 35 doses may be eligible for retreatment if they progress after stopping study treatment provided they meet the requirements detailed in section 5.3.5. Participants may be retreated in the Second Course Phase (Retreatment) for up to an additional 17 cycles (approximately 1 year).

After 35 dose administrations, patients can continue on treatment with eribulin alone.

Tumor assessments per RECIST v.1.1 (see **Appendix 2**) and irRECIST (see **Appendix 3**) will be performed approximately every nine weeks (\pm 7 days) for the first 12 months and every 12

weeks (\pm 7 days) thereafter until disease progression, treatment discontinuation, the start of new anti-cancer treatment, withdrawal of consent, death, or the end of the study, whichever occurs first. Tumor assessments will be performed on the specified schedule regardless of treatment delays.

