3.3.2 Treatment phase

Patients will receive study treatment according to the protocol and will be discontinued if one of the following situations arises:

- AEs which, according to the protocol or in the opinion of the Investigator, can cause serious or permanent damage or which rule out further treatment with the study drug.
- Disease progression is confirmed radiologically and unequivocally assessed according to the RECIST criteria version 1.1 and/or irRECIST.
- Major study protocol non-compliance.
- Patient's withdrawal from the study.
- Death.
- Study is canceled by the Sponsor.
- Completion of 35 treatments (approximately 2 years) with pembrolizumab. Please see section 5.3.5 of the protocol for the specific conditions.

Note: The number of treatments is calculated starting with the first dose. Participants who stop the combination or pembrolizumab after receiving 35 doses may be eligible for retreatment if they progress after stopping study treatment provided they meet the requirements detailed in section 5.3.5. Participants may be retreated in the Second Course Phase (Retreatment) for up to an additional 17 cycles (approximately 1 year).

After 35 dose administrations, patients can continue on treatment with eribulin alone.

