 - Conduction abnormality requiring a pacemaker.
 - Other cardiac arrhythmia not controlled with medication.

12. Uncontrolled hyper/hypothyroidism or T1DM. Patients with hypothyroidism stable on hormone replacement will not be excluded from the trial. Patients with controlled T1DM on a stable insulin regimen may be eligible for this study.
13. Active autoimmune disease that has required systemic treatment in the past 2 years (i.e., with use of disease modifying agents, corticosteroids, or immunosuppressive drugs).

Note: Replacement therapy (e.g., thyroxine, insulin, or physiologic steroid replacement therapy for adrenal or pituitary insufficiency, etc.) is not considered a form of systemic treatment.
14. Prior allogenic stem cell or solid organ transplantation.
15. Active/history of pneumonitis requiring treatment with steroids or active/history of interstitial lung disease.
16. Active uncontrolled infection at the time of screening.
17. Active tuberculosis.
18. Current known infection with HIV.
19. Active hepatitis B (HBV) [patients with negative hepatitis B surface antigen (HBsAg) test and a positive antibody to HBsAg (anti-HBsAg) test at screening are eligible] or hepatitis C (HCV) [patients with a positive antibody to hepatitis C (anti-HCV) are eligible only if polymerase chain reaction (PCR) is negative for virus hepatitis C RNA].
20. Patients have any other concurrent severe and/or uncontrolled medical condition that would, in the Investigator's judgment contraindicate patient participation in the clinical study.
21. Treatment with systemic steroids (standard premedication for chemotherapy/contrast reactions and local applications are allowed) or another immunosuppressive agent within seven days prior to study treatment initiation.
22. Has received live vaccines within 30 days prior to first dose of study treatment.
23. Women of child-bearing potential, defined as all women physiologically capable of becoming pregnant, are not allowed to participate in this study unless they are using highly effective methods of contraception during dosing and up to 120 days after study drugs discontinuation.

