5.2 Dosage and administration

The medicinal products should be administered sequentially on day 1 of each cycle (every three weeks) as follows: MK3475 (pembrolizumab) first followed immediately by eribulin. Eribulin will also be administered alone on day 8 of each cycle.

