5.3 Treatment modification

Safety and tolerability of all patients will be closely monitored throughout study treatment and the follow-up period using the NCI CTCAE v.4.0.3. Patients will be assessed in order to detect any AEs before administering new study treatment during each treatment visit. Treatment will only be administered if clinical evaluation and local laboratory test results are acceptable.

If, in the opinion of the Investigator, a toxicity is considered to be due solely to one component of the study treatment (e.g., MK3475 (pembrolizumab) or eribulin) and the dose of that component is delayed or modified in accordance with the guidelines below, the other component may be administered if there is no contraindication. When treatment is temporarily interrupted because of toxicity caused by MK3475 (pembrolizumab) or eribulin, the treatment cycles will be restarted such that the MK3475 (pembrolizumab) and eribulin infusions remain synchronized. Patients who have both treatments withheld for more than 21 days must discontinue study treatment and are considered off study. Patients whose treatment is interrupted or permanently discontinued due to an AE, including abnormal laboratory value, must be followed until resolution or stabilization of the event, whichever comes first, which includes all study assessments appropriate to monitor the event.

5.3.1 Modification of the amount of study drug administered due to changes in patient's weight

MK3475 (pembrolizumab) is administered as a fixed dose irrespective of the patient's body weight.

The amount of eribulin is calculated according to the patient's body surface area (BSA). Weight and height should be recorded at baseline and the BSA calculated, thereafter at every scheduled visit for all patients should be re-weighed. The amount to be administered must be recalculated if the patient's body weight has changed by > 10% (increased or decreased) from baseline. Recalculation based upon smaller changes in body weight or BSA are at Investigators' discretion.

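### Section 6.5.2 counts the 120-day contraception period from the last pembrolizumab dose only, so cover after a later eribulin dose is shorter than exclusion criterion 23 requires

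*Protocol*

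**What the plan says.** Two parts of the protocol set the end of contraception.

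- Section 6.5.2 starts birth control at screening and runs it "throughout the study period up to 120 days after the last dose of treatment with MK3475 (pembrolizumab". The same section opens by saying that "MK3475 (pembrolizumab) and eribulin may have adverse effects on a fetus in utero".
- Exclusion criterion 23 (section 4.3, and the same words in the synopsis) admits women of child-bearing potential only if they use "highly effective methods of contraception during dosing and up to 120 days after study drugs discontinuation".

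The dosing rules allow eribulin to be the last drug given.

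- Section 5.2: "Eribulin will also be administered alone on day 8 of each cycle".
- Section 3.1: the two drugs "may be discontinued for toxicity independently of each other in the absence of disease progression". Section 5.3 adds that when one component is delayed or modified for its own toxicity, "the other component may be administered if there is no contraindication".
- Section 3.3.2, and likewise section 3.1: "After 35 dose administrations, patients can continue on treatment with eribulin alone".

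**The concern.** The two rules agree only when pembrolizumab and eribulin are last given on the same day. Section 6.5.2 recognises a fetal hazard from both drugs, but the only post-treatment end point it states follows one of them. A site that works from section 6.5.2 alone could release a patient from contraception earlier than the sponsor's own 120 days after her last eribulin dose.

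The other pregnancy safeguards do not close this gap. Section 6.5.2 requires a test every two cycles and at the end-of-treatment visit, which takes place within 30 days of the last dose (section 3.3.3). Appendix 1 schedules no later test. Section 7.2 requires reporting of pregnancies up to 7 months after study drug discontinuation. These measures detect or record a pregnancy; they do not prevent one.

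The matter is one of participant safety and internal consistency. It does not touch the endpoint, sample size or analysis.

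**Working it through.** **Inputs**

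- Post-treatment period: 120 days (section 6.5.2 and exclusion 23).
- Cycle length: 21 days, with pembrolizumab on day 1 and eribulin on days 1 and 8 (section 5.2 and its subsections).
- Assumptions: no delays, and visit windows ignored. The number of eribulin-only cycles is illustrative, because the documents give no expected number.

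**Set-up**

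Let day 0 be the last pembrolizumab dose, on day 1 of cycle k. Eribulin in cycle k+j falls on days 21j and 21j + 7. If the last eribulin dose is on day t:

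- end date under section 6.5.2 = day 120
- end date under exclusion 23 = day t + 120
- gap between the end dates = t days
- cover left after the last eribulin dose under section 6.5.2 = 120 − t days, or none if t exceeds 120

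**Results**

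| Last eribulin dose | t | 6.5.2 ends | Exclusion 23 ends | Cover left under 6.5.2 |
|---|---|---|---|---|
| Cycle k, day 8 | 7 | day 120 | day 127 | 120 − 7 = 113 days |
| Cycle k+3, day 8 | 3 × 21 + 7 = 70 | day 120 | day 190 | 120 − 70 = 50 days |
| Cycle k+5, day 8 | 5 × 21 + 7 = 112 | day 120 | day 232 | 120 − 112 = 8 days |
| Cycle k+6, day 8 | 6 × 21 + 7 = 133 | day 120 | day 253 | none |

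The smallest gap is 7 days. It arises even when both drugs stop in the same cycle, provided that cycle's day-8 dose is given. Each further eribulin-only cycle adds 21 days. In the last row the stated end date comes before the last eribulin dose, so the pembrolizumab-based count supplies none of the 120 days after it.

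**What the opening words of the sentence cover**

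Section 6.5.2 also says that birth control runs through the study period. It does not define that term for this purpose, so both readings need checking.

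- If it means the time on study treatment, ongoing eribulin dosing is covered. The only end point given after dosing is still counted from pembrolizumab.
- If it means the whole study, section 3.3 includes a post-treatment phase, and section 3.3.4 places the end of study about 12 months after the last study dose (for first-course patients, worded by reference to the pembrolizumab course). That does not fit a limit of 120 days.

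Neither reading yields 120 days counted from the last eribulin dose. With the count taken from the later of the two drugs, section 6.5.2 would give the exclusion 23 dates in every row.

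**The case against.** The strongest reply is that the protocol already contains the right rule, twice, as a condition of participation. The sentence in section 6.5.2 is a recommendation. A patient who meets exclusion 23 also meets section 6.5.2, and nothing in section 6.5.2 expressly permits stopping earlier. This is largely right, and it is why the point is minor. It does not dispose of the point. Exclusion 23 is an entry criterion, and Appendix 1 schedules eligibility review at screening only. Section 6.5.2 is where site staff would look for when birth control starts and ends.

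A second reply is that the larger gaps are remote. The 35-dose route takes about two years, whereas the eribulin monotherapy trials cited in sections 1.3.2 and 1.3.3 had median progression-free survival of 2.6 to 4.1 months. The figure for the combination is unknown, so this is only suggestive, but it supports expecting few patients with long eribulin-only periods. It does not remove the 7-day gap or the toxicity route.

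Two stronger readings are tempting, and the documents do not support either.

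- A reader might infer that contraception lapses while eribulin is still being given, because the first dose after day 120 falls on day 126 (6 × 21). That ignores the reference to the study period, which on an ordinary reading includes ongoing eribulin dosing.
- A reader might infer that a 12-week pembrolizumab hold for unresolved toxicity (section 5.3.3), with eribulin continuing, leaves only 120 − 12 × 7 = 36 days. No site would start that count before knowing that the earlier pembrolizumab dose was the last.

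**Conclusion.** The inconsistency stands. Section 6.5.2 gives a shorter contraception period after the last eribulin dose than exclusion 23 does, whenever that dose falls on day 8 of the last combined cycle or later. The gap is at least 7 days and grows by 21 days per eribulin-only cycle. Once the last eribulin dose falls after day 120, the stated end point provides no cover after it. The defect is the length of cover after the last eribulin dose; it is not a lapse during dosing.

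The size rests on 21-day cycles without delays and on the sponsor's own 120 days as the benchmark. The documents give no contraception period specific to eribulin, so these figures do not estimate fetal risk. The number of patients affected is not given. It is likely to be small, because it requires childbearing potential and, for the larger gaps, several eribulin-only cycles. The consent form is not available here, so what patients are told is unknown and no failure in practice can be inferred. The textual mismatch itself is certain. It is a minor safety inconsistency that should be corrected because the remedy is so cheap.

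**What to change.** In section 6.5.2, replace the reference to the last pembrolizumab dose with the last dose of either study drug (pembrolizumab or eribulin), whichever is later. Leave exclusion 23 as it is, including its requirement for highly effective methods. Check that the consent form states the same end point.

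The cost is one phrase, made by written amendment or administrative letter with the approvals in section 12.2. The consent process in section 9.3 is needed only if the consent form has to change. There is no new visit, test or patient, and no effect on the analysis.
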